7.6 Criteria for Removal from Protocol Treatment

- a. Progression of disease or symptomatic deterioration (as defined in Section [10.5](#)) **for patients being treated with higher dose (56 mg/m²) carfilzomib.**
- b. Completion of 12 cycles of low dose carfilzomib on Arm 1 or 12 cycles of high dose carfilzomib.
- c. Unacceptable toxicity.
- d. Patient is unable to dose-escalate to assigned dose (27 mg/m² or 56 mg/m²) after 2 cycles of therapy.
- e. Permanent discontinuation of carfilzomib.
- f. Treatment delay for any reason > 4 weeks.
- g. The patient may withdraw from the study at any time for any reason.

7.7 Discontinuation of Treatment

All reasons for discontinuation of treatment must be documented in the Off Treatment Notice.

7.8 Follow-Up Period

All patients will be followed until death or 3 years after randomization, whichever occurs first.

8.0 TOXICITIES TO BE MONITORED AND DOSE MODIFICATIONS

8.1 NCI Common Terminology Criteria for Adverse Events

This study will utilize the CTCAE (NCI Common Terminology Criteria for Adverse Events) Version 4.0 for toxicity and Serious Adverse Event reporting. A copy of the CTCAE Version 4.0 can be downloaded from the CTEP home page (<http://ctep.cancer.gov>). All appropriate treatment areas should have access to a copy of the CTCAE Version 4.0.

8.2 General Considerations

- a. Missed doses are to be omitted rather than made up.
- b. If multiple toxicities are experienced, dose modifications will be based on the toxicity requiring the largest dose reduction.

- c. Reductions are based on the dose given in the preceding cycle and are based on toxicities observed since the prior toxicity evaluation.
- d. Once a dose is reduced, patients will continue at the new dose. No dose re-escalations are allowed.
- e. If carfilzomib must be permanently discontinued the patient will be removed from protocol therapy. See below for specific dexamethasone pre-medication instructions in the event of permanently discontinuing dexamethasone.

8.3 Dose Reductions for Toxicity

a. Carfilzomib

If a patient experiences any Grade 3 or 4 non-hematologic toxicity or Grade 4 hematologic toxicity in Cycle 1 that is considered to be related to study treatment, the second cycle of treatment will be given with carfilzomib at 20 mg/m^2 prior to escalation to the respective treatment dose for subsequent cycles. If a patient cannot undergo the dose escalation to the treatment dose despite being at 20 mg/m^2 for 2 cycles, they will be removed from protocol therapy.

Patients experiencing \geq Grade 3 non-hematologic or Grade 4 hematologic toxicity considered related to carfilzomib will have their treatment held until toxicity has resolved to Grade 2 or better. Supportive care should be administered per local institutional guidelines. When the toxicity has resolved, treatment will resume per the following guidelines:

- If the toxicity is resolved with supportive care prior to the next scheduled dose, carfilzomib treatment will be resumed at the same dose level.
- If the toxicity does not resolve until after the next scheduled dose, carfilzomib will be resumed at the next lower dose level as outlined in the dose reduction table below.

	Arm 1	Arms 2 and 3
Assigned Dose	27 mg/m^2	56 mg/m^2
Dose Level -1	20 mg/m^2	45 mg/m^2
Dose Level -2	15 mg/m^2	36 mg/m^2

- For patients whose drug toxicity does not resolve to Grade 1 or better (with the use of adequate supportive care) after 4 weeks of holding treatment, or who experience \geq Grade 3 non-hematologic or Grade 4 hematologic toxicity at Dose Level -2 will be removed from protocol treatment.

b. Dexamethasone

In general, dose reduction of dexamethasone is not allowed. However, in the case of Grade 3 or 4 gastrointestinal bleeding, dexamethasone may be discontinued, depending on clinical judgment of the treating physician. In case of dexamethasone discontinuation, premedication guidelines as mentioned below should be used and carfilzomib therapy will continue. For other Grade 3 or 4 toxicities with dexamethasone (including Grade 3 or 4 hyperglycemia despite adequate treatment with anti-hyperglycemic measures including insulin) rather than discontinuing the drug, dose may be reduced by up to 50% if side effects persist despite administration of supportive care per local institutional standards.

If the dexamethasone cannot be administered even at a 50% dose reduction, pre-medication with dexamethasone 4 mg intravenously should be given prior to all doses of carfilzomib during Cycle 1 and prior to all carfilzomib doses during the first cycle of dose escalation to 27 mg/m² (Arm 1) or 56 mg/m² (Arms 2 and 3) to reduce the incidence and severity of any infusion reactions. Dexamethasone premedication (4 mg intravenously) will be reinstated if these symptoms develop or reappear during subsequent cycles.

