7.2 Pre-Medication

Prior to each dose in Cycle 1, 250-500 mL of intravenous normal saline will be given to reduce the risk of renal toxicity and of tumor lysis syndrome (TLS). An additional 250-500 mL of intravenous fluids as needed may be administered following carfilzomib administration, at the discretion of the treating physician. Intravenous hydration, as needed, may be given in subsequent cycles. Patients should be monitored during this period for fluid overload. Patients should not receive a total of more than 1 liter of intravenous hydration per administration. In the event of patient crossover to Arm 3, Cycle 1 intravenous hydration can be administered at physician discretion.

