7.4 Registration Step – Crossover Registration (Arm 3)

Note that patients who cross over from Arm 1 to Arm 3 must be registered to Step 2 prior to initiation of cross-over treatment on Arm 3.

Agent	Dose	Route	Day	Schedule*
Dexamethasone ^b	20 mg	IV	1, 2, 8, 9, 15, 16	up to 12 cycles
Carfilzomib ^a	56 mg/m ²	IV over 30 mins	1, 2, 8, 9, 15, 16	Cycles 1-12

* Note: 1 cycle = 28 days

^a For Arm 3, Cycle 1 carfilzomib dosing is not reduced, but given at the full 56 mg/m² (see Section 7.3a for dose capping based on BSA).

^b On all treatment days, dexamethasone will be administered 30 minutes prior to the carfilzomib infusion.

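### The Cycle 1 toxicity rule in protocol 8.3a lacks the Arms 1 and 2 limit it has in 7.3a, so taken as written in Arm 3 it conflicts with the dose table and with 8.2d (minor)

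*Combined protocol and SAP*

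**What the plan says.** Section 7.3 covers the initial registration, Arms 1 and 2. Under 7.3a both arms start at 20 mg/m² in Cycle 1 and rise to 27 or 56 mg/m² from Cycle 2. It then gives a rule for severe related toxicity in Cycle 1.

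Section 8.3a repeats that rule without naming an arm: "If a patient experiences any Grade 3 or 4 non-hematologic toxicity or Grade 4 hematologic toxicity in Cycle 1", if related to study treatment, means a second cycle at 20 mg/m² "prior to escalation to the respective treatment dose for subsequent cycles". The next sentence removes certain patients: "If a patient cannot undergo the dose escalation to the treatment dose despite being at" 20 mg/m² for 2 cycles.

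Section 8.3a then gives a general hold-and-resume rule for severe toxicity related to carfilzomib. If it resolves before the next scheduled dose, "carfilzomib treatment will be resumed at the same dose level". If not, "carfilzomib will be resumed at the next lower dose level as outlined in the dose reduction table below". The table has one column for Arm 1 (27, 20, 15 mg/m²) and one for Arms 2 and 3 (56, 45, 36 mg/m²). Section 8.2d adds: "Once a dose is reduced, patients will continue at the new dose. No dose re-escalations are allowed".

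For crossover patients, 7.4 schedules Arm 3 as Cycles 1 to 12 and says "For Arm 3, Cycle 1 carfilzomib dosing is not reduced, but given at the full" 56 mg/m². Footnote 19 of the study calendar (9.0) returns these patients to Cycle 1, Day 1.

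**The concern.** In Arms 1 and 2 the Cycle 1 rule delays a first escalation. Arm 3 has no 20 mg/m² lead-in, so there the same words prescribe a steep cut followed by a return to the dose at which the toxicity occurred. A site using Section 8 for an Arm 3 patient would find two rules for one event, at that patient's first exposure to 56 mg/m², and would have to work out which applies.

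Elsewhere the protocol states it when a Cycle 1 rule differs in Arm 3. Section 7.2 does so for fluids ("In the event of patient crossover to Arm 3, Cycle 1 intravenous hydration can be administered at physician discretion") and 7.4 does so for the starting dose. Section 8.3a has no such statement.

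At stake are the safety of the affected crossover patients and the crossover response rate, which 11.5 uses to ask whether a higher dose recaptures response.

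**Working it through.** The plan gives no figure for this point. The check compares dose paths and then bounds the number of patients.

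**1. Dose path after a related Grade 3–4 non-hematologic or Grade 4 hematologic toxicity in Cycle 1**

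| Rule | Cycle 1 | Cycle 2 | Cycle 3 on |
|---|---|---|---|
| Cycle 1 paragraph, Arm 1 or 2 | 20 | 20 | 27 or 56 |
| Cycle 1 paragraph, taken as written in Arm 3 | 56 | 20 | 56 |
| Hold-and-resume, Arm 3, resolved before next dose | 56 | 56 | 56 |
| Hold-and-resume, Arm 3, resolved later | 56, then 45 | 45 | 45 |
| Hold-and-resume, Arm 3, two reductions in Cycle 1 | 56, then 45, then 36 | 36 | 36 |

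Doses are in mg/m², and the hold-and-resume rows assume no further toxicity. In the first row nothing is reduced and then raised again, so 8.2d is not engaged. In the second row the dose leaves the Arm 3 table and then rises again, against 8.2d. The conflict is therefore confined to Arm 3.

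**2. Size of the difference in Arm 3 Cycle 2**

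Dosing is on Days 1, 2, 8, 9, 15 and 16, so 6 doses per cycle (7.4).

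- Cycle 1 paragraph: 6 × 20 = 120 mg/m²
- Hold-and-resume: 6 × 56 = 336, 6 × 45 = 270, or 6 × 36 = 216 mg/m²
- Ratios: 120/336 = 36%; 120/270 = 44%; 120/216 = 56%

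The dose from the Cycle 1 paragraph is thus 56% of the lowest level that the Arm 3 table allows.

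**3. How many patients could be concerned**

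Inputs: 63 eligible patients planned in Arm 1, a 9-month median PFS and exponential progression times (all 11.2). Crossover requires progression before completing 12 cycles (5.2a), with 28-day cycles (7.3b).

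- Duration: 12 × 28 = 336 days; 336/30.44 = 11.04 months
- Proportion with a PFS event by then: 1 − exp(−ln 2 × 11.04/9) = 1 − 0.427 = 0.573
- Expected number: 63 × 0.573 ≈ 36

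The 36 includes deaths, and deaths cannot cross over. Section 5.2 also requires that Cycle 2 was begun, a gap of 14 to 28 days since the last Arm 1 treatment, recovery from toxicity, no toxicity reduction in the last cycle and an acceptable ejection fraction. Of those who cross over, only patients with a qualifying toxicity in Arm 3 Cycle 1 meet the conflict. The documents give no rate for these later steps, so the planning range is 0 to about 36, with the true figure well inside it.

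**The case against.** The strongest reply is that the paragraph limits itself. Only a patient who started at 20 mg/m² can have spent two cycles at 20 by the end of Cycle 2, so the removal sentence cannot describe an Arm 3 patient. Section 7.6d, on failure to escalate after two cycles of therapy, points the same way. Section 7.4 sends Arm 3 to 7.3a only for the body-surface-area cap. A reading that goes to a dose outside the table, breaks 8.2d and leaves the next sentence without application is not what the authors meant. A site in doubt could also use the dose-modification contacts listed as Section 8.5.

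Most of this stands. The intent is Arms 1 and 2 only, and a careful reader can find the cue in 8.3a itself as well as in 7.3a. It does not remove the conflict, for three reasons.

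- The sentence that sets the dose carries no limit. The cue is in the sentence about removal.
- The word escalation does not exclude Arm 3, because 8.3b itself speaks of escalating to 56 mg/m² in Arms 2 and 3.
- It might be said that footnote 19 restarts the cycle count only for assessments. But 7.4 itself numbers Arm 3 treatment from Cycle 1.

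The contact route helps only a site that notices the conflict.

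A reader might go further and infer that the plan means to drop Arm 3 patients to 20 mg/m², or that patients were dosed this way. The documents support neither: the wording points to the opposite intent, and there is no record of Arm 3 dosing. Nor should all 63 Arm 1 patients be counted as exposed, since crossover needs progression within 12 cycles.

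**Conclusion.** This is a minor wording conflict in a dosing rule. Section 8 does not state the limit that 7.3a gives the same text, and for Arm 3 the paragraph as written yields a Cycle 2 dose of 36% to 56% of what the other rules give, followed by a return to 56 mg/m². It deserves correction because a stated rule gives a wrong dose, even though the right one can be inferred.

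The ceiling of about 36 patients is an expected number. It rests on the planned exponential PFS with a 9-month median, 63 eligible Arm 1 patients and cycles given on schedule.

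It would be wrong to infer any effect on the primary comparison. Arm 3 treatment begins after the Arm 1 progression that counts as the PFS event (10.5), so primary PFS, power, alpha and event counts do not change.

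**What to change.** Two edits to 8.3a:

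1. Begin the Cycle 1 paragraph with: *Arms 1 and 2 only.*
2. Add: *Arm 3: toxicity in any cycle, including Cycle 1, follows the hold-and-resume rules and the table below (56, 45, 36 mg/m²).*

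The cost is one label and one sentence, with no added visits, data or patients. Accrual is permanently closed, but that does not by itself end treatment or crossover for patients already enrolled. A memorandum at the front of the protocol already promises a next revision to correct 11.8, and these edits can go in with it.

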 - ✓ Respiratory, Thoracic and Mediastinal Disorders: Pulmonary toxicities: Interstitial Lung Disease (including pneumonitis), Acute Respiratory Failure and Acute Respiratory Distress Syndrome (ARDS)
 - ✓ Vascular Disorders: Stroke
- The following risks were removed:
 - Less Likely(4-≤20%):
 - ✓ Psychiatric Disorders: Confusion and Mental status change
 - ✓ Skin and Subcutaneous Tissue Disorders: Dry Skin
 - Rare but Serious (≤3%):
 - ✓ Renal and Urinary Disorders: BUN increased
- The following risk was moved from Rare but Serious (≤3%) to Less Likely(4-≤20%):
 - Cardiac Disorders: Congestive Heart Failure
- The following risk was moved from Likely (>20%) to Less Likely(4-≤20%):
 - Musculoskeletal and Connective Tissue Disorders: Chest pain

4. Page 29, Section 8.3a: The carfilzomib dose reduction for toxicity has been adjusted to allow treatment to be resumed in event that patients experience a \geq Grade 3 non-hematologic or Grade 4 hematologic toxicity that is considered related to carfilzomib provided that the toxicity has resolved to Grade 2 or better (instead of resolution to Grade 1 or better, as previously indicated).

5. Page 31, Section 9.0: The "9" in column C7 for Serum β 2 Microglobulin was a typographical error, and has been removed.

6. Page 33, Section 9.0: The following clarifications have been made to footnotes (9) and (13)

- Footnote (9): A sentence has been added to the end of this footnote to clarify that, "Crossover patients do not need to repeat Cycle 1, Day 1 tests as long as patient is starting Arm 3 treatment within 28 days of prior testing (at time of progression) and the previous test results did not show a significant change from baseline."
- Footnote (13): The last sentence of this footnote has been modified to clarify that response assessments are no longer required for study purposes once a patient has been removed from the trial due to toxicity.

SWOG considers that the Model Consent Form changes **do not** represent an alteration in risk/benefit ratio. Therefore, local accrual does **not** need to be suspended pending implementation of these changes.

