- 11 Pre-study (within 14 days prior to registration), then on Day 1 (\pm 3 days) of Cycles 2-12, then monthly until disease progression, at disease progression and at all follow up visits.
- 12 See Section [15.2](#).
- 13 Every 3 months after removal from protocol therapy for up to 3 years after initial registration, or more often if clinically indicated. For study purposes, response assessments (SPEP, immunoglobulins, 24 hour urine, serum/urine IFE, and CRP) are no longer required after progression or removal from trial due to toxicity.
- 14 See Section [7.0](#).
- 15 See Section [8.5](#) for treatment modification for cardiopulmonary events.
- 16 Unless otherwise noted, all required studies are to be performed on Day 1 of the treatment cycle.
- 17 At the time of progression, patients on Arm 1 may cross-over to Arm 3, providing they meet the additional criteria outlined in Section [5.2](#).
- 18 For patients with extramedullary progression (EMP), a follow-up PET scan at the end of treatment or at the time of VGPR, whichever occurs earlier, is required. See Sections [15.1](#) and Appendix [18.2](#) for requirements.
- 19 For patients that crossover to Arm 3, return to Cycle 1, Day 1, and follow the same study calendar. Assessments completed at time of progression on Arm 1, do not need to be repeated on Arm 3 (crossover) C1, D1, provided that ANC, platelets, SGOT, SGPT, serum creatinine, SPEP, and lambda light chain assessments are accomplished within 14 days prior to registration to Arm 3. All other assessments may have been accomplished anytime within 28 days prior to registration to Arm 3 (i.e. at time of progression on Arm 1). Note: Per eligibility criterion 5.2b, at least 14 days and no more than 28 days must have elapsed between the last day of treatment on Arm 1 and registration to Arm 3.

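### Section 8.3a uses two different recovery grades for the same carfilzomib hold, so a patient at Grade 2 at about the 4-week point is told both to resume and to come off treatment

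*Combined protocol and SAP*

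**What the plan says.** Section 8.3a covers related toxicity of Grade 3 or higher (non-hematologic) or Grade 4 (hematologic). Such patients "will have their treatment held until toxicity has resolved to Grade 2 or better". The text goes on: "When the toxicity has resolved, treatment will resume per the following guidelines". Two bullets then set the dose at restart. Toxicity that clears before the next scheduled dose means the same dose level; toxicity that clears later means one level lower.

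The final bullet of that list says that a patient whose toxicity "does not resolve to Grade 1 or better (with the use of adequate supportive care) after 4 weeks of holding treatment" "will be removed from protocol treatment". A second limb of this bullet, on recurrent severe toxicity at the lowest dose level, is not in question here.

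Two other places bear on the point. Section 7.6f lists as a reason for removal: "Treatment delay for any reason > 4 weeks". Footnote 13 of the Section 9.0 study calendar says that response assessments "are no longer required after progression or removal from trial due to toxicity".

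**The concern.** Restarting and removal are the two ways out of one hold, so they should turn on one definition of recovery. Here the way back into treatment is Grade 2 and the way out is failure to reach Grade 1. A patient at Grade 2 meets the first condition and also fails the second.

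The rule governs retreatment after severe drug-related toxicity, so sites need a single instruction. If sites differ, recorded removals for toxicity will partly reflect which sentence each site followed. The same ambiguity can affect the dose at restart. Section 8.2d forbids re-escalation, and Section 5.2d bars crossover from Arm 1 after a toxicity reduction in the last cycle before progression, so a reduction made on one reading and not the other has lasting effects.

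**Working it through.** No sample size, power or event count is involved. The check sets the rules side by side.

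**Inputs**
- Restart rule, Section 8.3a: the hold ends at Grade 2 or lower, and treatment resumes.
- Removal rule, Section 8.3a, last bullet: removal if the toxicity is not at Grade 1 or lower after 4 weeks of holding.
- Delay rule, Section 7.6f: removal if the delay exceeds 4 weeks, with no reference to grade.

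**At the 4-week point, by grade**

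| Grade at 4 weeks | Restart rule | Removal rule | Result |
|---|---|---|---|
| 0 or 1 | Resume | Not removed | Consistent |
| 2 | Resume | Removed | Contradictory |
| 3 or higher | Still held | Removed | Consistent |

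Section 7.6f does not decide the Grade 2 row, because it needs a delay of more than 4 weeks.

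**Before 4 weeks.** A patient who reaches Grade 2 in week 1, 2 or 3 satisfies the restart rule. Treatment resumes and the hold is over, so the 4-week condition in the removal bullet is never met. On this strict reading there is no clash. A softer ambiguity remains. The Grade 1 wording sits in the list that says how treatment restarts, so a site could take Grade 1 as the meaning of resolved throughout. Take a patient who reaches Grade 2 before the next scheduled dose and Grade 1 only after it. With recovery read as Grade 2, the dose level is unchanged; with recovery read as Grade 1, it drops one level.

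**After 4 weeks.** Section 7.6f removes the patient whatever the grade, so the two sentences of 8.3a no longer lead to different outcomes.

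**Clocks.** This comparison takes the 8.3a hold and the 7.6f delay as starting together. Neither section defines its start. If the delay were counted from the first missed dose and the hold from an earlier day, the overlap at Grade 2 would last for the days between the two.

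**Source of the mismatch (context only).** The Revision #5 summary records that resumption was allowed "provided that the toxicity has resolved to Grade 2 or better (instead of resolution to Grade 1 or better, as previously indicated". It does not mention the removal bullet. That summary is not evidence of error; the conflict stands within the current text of 8.3a alone.

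**The case against.** The strongest reply is that the sentences work in sequence. The removal bullet applies only to patients still held at 4 weeks, and anyone who reached Grade 2 earlier is no longer held. Beyond 4 weeks, 7.6f settles the matter. This is largely right, and it confines the direct conflict to about the 4-week point. It does not remove the conflict there, and it does not explain why two grades are used. A deliberate two-step rule, with restart at Grade 2 and later removal if Grade 1 is not reached, would need different words, because the bullet counts weeks of holding and not weeks since onset.

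Three stronger readings are tempting, and the documents do not support them.

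- A reader might infer that every patient who settles at Grade 2 is both retreated and removed. Most such patients would restart before week 4 and never meet the removal condition. A count of everyone who settles at Grade 2 would therefore measure the wrong group, and the documents give no rate for it in any case.
- A reader might infer that the choice of grade decides who is followed for progression-free survival. Footnote 13 drops the required response tests after removal for toxicity. However, Section 7.8 follows all patients until death or 3 years, Section 14.4 requires a form every 3 months off treatment and documentation of progression found off treatment, and Section 10.5 counts death as an event. Assessment may become less intensive, but follow-up does not stop. Any bias from footnote 13 arises for every toxicity removal, whichever grade 8.3a uses.
- A reader might infer that removals will be unequal between arms because the higher dose causes more holds. The Section 2.0 rationale expects no significant additional toxicity at the higher dose, and Section 11.7 tests for an excess in Arm 2 without predicting one. An imbalance is possible but not shown.

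**Conclusion.** The point holds in a narrow form. Section 8.3a contains two inconsistent recovery grades for one hold. They give opposite instructions for a patient at Grade 2 at about 4 weeks, and no other section resolves this. There is a secondary ambiguity before week 4 about what counts as resolved, which can affect whether the dose is reduced.

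The number of patients affected cannot be derived from the documents. It is probably small, since a patient must still be held at about 4 weeks and be at Grade 2 then. This rests on the strict sequential reading and on the two 4-week clocks starting together.

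The point does not touch the significance level, the power or the intent-to-treat population in Section 11.3. It is a wording inconsistency in a retreatment rule that is worth correcting, and not a threat to the primary analysis. Accrual is permanently closed, so the correction matters for any patients still on treatment and for interpreting removals already recorded.

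**What to change.** The study team should reconcile the hold-and-resume sentence and the removal bullet of Section 8.3a with each other and with Section 7.6f, so that one definition of recovery governs both restart and removal. The same edit should make clear that this definition applies in the two bullets on the dose at restart, and should say when the 4-week periods in 8.3a and 7.6f begin. This review does not say which grade is right. The cost is a short text clarification and a memorandum to sites; no analysis or sample-size change follows.
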